The purpose is to investigate the relationship between high total intake of systemic steroids in patients with upper and lower airway disease, low endogenous cortisol production, and reduced bone density and structure. Additionally, through an exploratory follow-up (pilot project) study, to investigate whether improved adherence to local steroid treatment and biologic medication would decrease the patient's endogenous cortisol production.

Hypothesis/research question:

Patients with CRS/CRSnNP/CRSwNP who have received systemic steroids have an impact on the adrenals with low basal P-cortisol (below 500nmol), abnormal response to stimulation with ACTH (synacthen test) measured at the final P-cortisol. Additionally, a reduced increase (delta value) in P-cortisol is expected in connection with a synacthen test. These patients also have an affected bone density and structure with a higher incidence of osteopenia and osteoporosis than expected for this age group. Patients with CRS/CRSnNP/CRSwNP who can improve their adherence to >80% have an increasing impact on P-cortisol.

Primary outcome:

The primary outcome is to investigate whether newly referred patients with upper and possible lower respiratory tract diseases have an impact on their own cortisol production after prolonged use of systemic steroids. That is, the baseline level of plasma cortisol is <500 nmol, and a correlation with lifelong use of systemic steroids can be demonstrated.

Secondary outcomes:***Cross-sectional study:***

- 1: After a stimulation test, plasma cortisol is not above 500 nmol.
- 2: The increase in plasma cortisol is associated with the intake of systemic steroids.
- 3: Demonstration of the correlation between lifelong use of systemic steroids and the degree of osteopenia and osteoporosis (T-score). T-score from DEXA scanning is used to measure bone density and structure. An affected T-score is defined as follows: T-score between -1.0 and -2.5 = osteopenia and score \leq -2.5 = osteoporosis.
- 4: The number of patients with osteoporosis/penia of the spine and femur is increased compared to expected findings in age-matched individuals.

Exploratory follow-up at 4 months (pilot project):

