- 5: Patients with CRSwNP/CRSsNP/CRS with and without asthma who have shown low adherence <80% after the cross-sectional study and who have achieved adherence over 80% at follow-up have also developed adrenal function impairment with a reduction in plasma cortisol of at least 8% (exploratory study).

Study design (brief description):

The study design is a cross-sectional study of newly referred patients to the Luftvejsklinik, ENT, RH for investigation and treatment of CRS and possibly asthma. And an exploratory follow-up (pilot project) study of patients who attend 4-month control.

Background:

Chronic rhinosinusitis (CRS) is a condition with chronic inflammation in the nose and sinuses. CRS can be with both nasal polyps (CRSwNP) and without polyps (CRSsNP) (5). 9% of the Danish population is affected by CRS, and about 4% are estimated to be diagnosed with CRSwNP (1). The diagnosis is based on the patient's symptoms and objective signs of inflammation in the nose and sinuses. The symptoms are a blocked nose or nasal secretion, reduced airflow, reduced sense of smell, pain/pressure around the nose, forehead, or eyes. The above symptoms must have been present for more than 12 weeks, and one of the symptoms must be secretion or reduced airflow through the nose to make a diagnosis (6). About 40% of CRS patients in primary care have asthma, whereas 65% referred for treatment at the hospital have asthma (7). CRSwNP that is not satisfactorily controlled particularly affects quality of life (8). It is often characterized by type-2 inflammation, i.e., an increased number of eosinophils in the mucous membranes in the sinuses and nasal polyps - as well as comorbidities such as asthma, ASA/NSAID intolerance (N-ERD), and allergies (5). CRS can be treated both surgically and medically. The basic medical treatment of CRS includes daily saline irrigation and use of nasal steroids. If there is a lot of secretion, antibiotic treatment can also be added to the basic treatment. In the case of nasal polyps, systemic corticosteroid treatment (prednisolone tablets/injection betamethasone) can also be added (5,6). If the medical treatment is not

optimal, patients can be offered surgical treatment - endoscopic sinus surgery (ESS) (5). The goal is to aim for the removal of polyps in the nose and sinuses.

Comorbidity:

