The use of steroids is a part of medical treatment for CRSwNP and asthma, and systemic steroid use is often seen in moderate to severe cases. It can affect the body's own production of hormones, which at different doses can trigger adrenal insufficiency. The condition is divided into primary and secondary adrenal insufficiency (22). Primary adrenal insufficiency involves the body's reduced or complete lack of hormone-producing cells in the adrenal cortex. Secondary adrenal insufficiency is caused by reduced production or effect of ACTH from the pituitary gland in the brain (2, 22, 23). The most common form of secondary adrenal insufficiency develops during external steroid treatment with pharmacological doses for a non-endocrine disease, such as CRSwNP and asthma. About 25% of patients receiving long-term steroid treatment develop long-term adrenal insufficiency - the higher the dose and treatment duration, the greater the risk (2, 23). Adrenal insufficiency can also occur with locally administered steroids - for example, it has been shown that 8% of patients treated with inhaled steroids, 52% after intramuscular injection, and more than a third of patients in long-term low-dose steroid treatment develop insufficiency (23, 24). In addition, steroid creams have been shown to have systemic side effects in a previously unknown high number of patients (3). Reduced production of steroids from the adrenals is a situation that should be considered in connection with acute illness, but also surgery (22, 25). Many patients with CRSwNP are offered 1-3 injections of steroids annually, in addition to high doses of nCS. Surgical intervention is also performed in between these injections. Here, one could consider supplementing preoperatively with steroids as protection against the stress of surgery if the endocrine axis is affected. Systemic glucocorticoids are used as treatment for a wide range of diseases, such as inflammatory diseases like CRSwNP or asthma either as needed or chronically (26-28). Glucocorticoid-induced osteoporosis is the most common secondary cause of osteoporosis and is a global public health problem, where fractures contribute to significant morbidity and mortality (29). The frequency of secondary glucocorticoid-induced osteoporosis is unknown in patients with CRSwNP (26). Prevention of this and negative consequences should be a focus point for healthcare professionals in these patients due to long-term treatment with systemic glucocorticoids (28).

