The Synacthen test is performed by inserting a venous catheter at time 0, and then a blood sample is taken to determine the plasma cortisol level. Subsequently, 0.25 mg of ACTH is injected into the venous catheter, and 5 ml of iso NaCl is flushed. After 30 minutes, a blood sample is taken to determine the plasma cortisol level. The first mL should be discarded before obtaining a new P- Cortisol is taken. The 0-sample and 30-sample belong to the same Sampling Test Form (PTB). Scanned with PDA corresponding to the actual sampling time. The blood samples are sent together with their corresponding PTBs for analysis at the Clinical Biochemical Department, RH. Results will appear in the patient's medical record under laboratory results. The patient must not have ingested hydrocortisone or steroid inhalation at least 12 hours before the test and should not have received treatment with injection (i.m) steroid such as diprospan within the last three months (30). The entire procedure for the synacthen test takes approximately 1 hour and 15 minutes, including preparation and completion. The test itself takes about 30 minutes. This applies to both the cross-sectional study and exploratory follow-up.

DEXA scan:

Patients with CRS/CRSsNP/CRSwNP receive a DEXA scan as part of their clinical evaluation. This group has received larger amounts of nasal steroid for often more than 10 years, as well as 1-3 times systemic steroid annually over several years. Therefore, it is good clinical practice to refer to a DEXA scan to examine bone density and structure and any need for treatment with calcium and vitamin D. These investigations are included in the project.

Questionnaires:

Patients are required to complete the following questionnaires as part of the standard treatment in the Respiratory Clinic:

- STARR-15
- SNOT-22:
- ACQ
- ACT
- MARS 5-L/N:
- Foster score

Data processing:

Data will be entered into REDCap (Research Electronic Data Capture), which is a secure web application for building and managing databases and online questionnaires. The system was developed at Vanderbilt University, which released the first version in 2008 (31). The use of REDCap is a requirement from Region Hovedstaden.

Statistical analysis:

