Statistical analysis of the data will be performed using IBM SPSS Statistics. Results will be presented as mean, SD, median, range, and 95% CI. Parametric data will be compared using paired tests, and non-parametric data using Mann-Whitney Test. Categorical variables will be tested using the chi-square test.

Power calculation for cross-sectional study and exploratory follow-up at 4 months (pilot project):

Rationale: In a recent study on severe asthma, patients received daily tablet prednisolone (>5 mg) for 3 months. 60% of the patients had adrenal insufficiency, 33% had total insufficiency, and 27% had partial insufficiency (32). Patients with CRS are often treated with steroid injections in Denmark, receiving an average of three steroid injections per year (clinical observation, REDCap, Global airways incl. biological treatment). Some receive up to six injections per year, with an effect lasting approximately 6-8 weeks per injection. This means that patients with CRS are only covered for about 6 months out of 12 months per year. This is different from severe asthma with daily treatment. Therefore, we estimate that we can detect half of the findings from the asthma study (32). We therefore expect that half of the 60% who develop insufficiency in the asthma study = 30% of the CRS patients will have adrenal insufficiency. As some will have received steroid injections several months ago, a slight reduction is estimated to 25%. But no less than 25%, as many receive high-dose nasal steroids, which, like steroid cream, may cause adrenal insufficiency (3). The 25% is our best estimate. It may be higher but not lower. The literature has documented that 8% of a population have adrenal insufficiency without having received supplemental steroids before the test. To

demonstrate a difference between the background population and our population with 25% adrenal insufficiency, we will need to investigate 72 patients with an alpha value of $p < 0.05$ and a power of 80%, and with a dropout rate of 10%, we will need to test around 80 patients (cross-sectional study).

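### The pre-test rule for the Synacthen test does not cover prednisolone tablets, so current dosing can be mixed with lifelong steroid use in the primary outcome

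*Protocol*

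**What the plan says.** The protocol's Synacthen test section gives the pre-test rule in one sentence with two parts. For short-acting exposure: "The patient must not have ingested hydrocortisone or steroid inhalation at least 12 hours before the test". For depot injections, the patient "should not have received treatment with injection (i.m) steroid such as diprospan within the last three months". The sentence cites the hospital's own Synacthen instruction (reference 30), and the section says that the procedure applies to both the cross-sectional study and the follow-up.

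The Background section describes how nasal polyps are treated in this population: "systemic corticosteroid treatment (prednisolone tablets/injection betamethasone) can also be added". The Introduction adds that referred patients go on receiving steroids because of their disease burden.

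The eligibility lists, in the Protocol Summary and again under Study population, exclude patients who have never taken systemic steroids. They set no limit on current or recent use.

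The primary outcome requires that "the baseline level of plasma cortisol is <500 nmol, and a correlation with lifelong use of systemic steroids can be demonstrated". The Method section says that the total amount of systemic steroid will be calculated and that the first test takes place at the first visit.

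**The concern.** The two systemic routes that the Background names together are handled differently. Injections must be three months past. Tablets have no condition at all, unless the tablet is hydrocortisone. The protocol does not explain the difference.

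This matters because the primary outcome is read from the 0-minute sample and interpreted as a consequence of lifelong use. The protocol itself says that the most common form of "secondary adrenal insufficiency develops during external steroid treatment with pharmacological doses for a non-endocrine disease, such as CRSwNP and asthma". A low basal value taken during a tablet course may therefore reflect the present dose, the accumulated past, or both. The plan as written gives no means of telling these apart. The current course is also part of the lifelong total, so it enters both variables of the correlation.

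The concern is attribution. A low cortisol in a patient on tablets is still clinically useful to know, for instance before surgery.

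**Working it through.** No figure in the plan is disputed. The check sets the rule beside the treatments it should cover, and then asks what follows for each half of the primary outcome.

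**1. Which routes does the rule cover?**

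| Exposure | Named as treatment here | Condition before the test |
|---|---|---|
| Hydrocortisone by mouth | not named as a CRS treatment | at least 12 hours |
| Inhaled steroid | yes, in asthma | at least 12 hours |
| Intramuscular steroid | yes | three months |
| Prednisolone tablets | yes | none stated |

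Neither the eligibility criteria nor any other section fills the last row.

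**2. What does the injection window do?** The Power calculation section describes injections "with an effect lasting approximately 6-8 weeks per injection". Three months is 3 × 365.25 / 12 / 7 = 13.0 weeks. The margin is 13.0 − 8 = 5.0 weeks to 13.0 − 6 = 7.0 weeks. For injections, then, the rule removes current effect before the sample is taken. This shows that the protocol treats recent systemic exposure as something to clear. It does not say how long a tablet window should be. The same section, comparing intermittent injections with daily tablets, says "This is different from severe asthma with daily treatment", so the authors regard current daily dosing as a distinct state.

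**3. Proportion below 500 nmol.** Assume that a current course can only lower the basal value. If k of n tested patients are on tablets, the observed proportion can exceed the value without those courses by at most k/n. With n = 80, each such patient contributes at most 1/80 = 1.25 percentage points; with n = 72, at most 1/72 = 1.39 points. The documents do not give k. As assumed values only, k = 4 of 80 gives a ceiling of 5 points and k = 8 of 80 a ceiling of 10 points. A patient who would be below 500 nmol anyway contributes nothing, so the true effect may be far smaller, or zero.

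**4. Correlation with lifelong intake.** Let Y be basal cortisol, L the lifelong total, and C = 1 for a patient on a current course. Suppose

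Y = a − bL − dC + e, with d > 0.

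Write C = c₀ + gL + r, where g = Cov(L, C) / Var(L) and r is uncorrelated with L. Substituting,

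Y = constant − (b + dg)L − dr + e.

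Two effects follow.
- The slope on L changes from −b to −(b + dg). If current users have higher lifelong totals (g > 0), the association looks stronger. If they have lower totals (g < 0), it looks weaker.
- The residual variance rises by d²·Var(r), which weakens the correlation whatever the sign of g.

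Split L into past use P plus the current course, of dose D (taken as equal for all). Then Cov(L, C) = Cov(P, C) + D·Var(C). The second term is never negative, but one course may be small against a lifetime of use, and Cov(P, C) can have either sign. The net direction is not determined by anything in the protocol.

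**The case against.** The strongest reply is that the sentence summarises a governing document. It cites the hospital's Synacthen instruction, and the Protocol Summary, under side effects and risks, says that the test follows the endocrinology department's recommendations. If that instruction already covers prednisolone, patients on tablets may never be tested in practice. This cannot be checked, because the instruction is not at hand. If it is wider, the protocol sentence is narrower than its source and should be aligned with it. That reduces the practical risk but does not correct the text.

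A second reply is that tablets may be uncommon at the test. The Background says only that they can be added, and the Power calculation section describes injections as the usual systemic route. This stands: no share is given, and the size is therefore unknown.

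A third is that low cortisol during treatment is part of what the study sets out to find. This stands for the clinical question, but not for a primary outcome worded as a correlation with lifelong use.

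A fourth is that flags and sensitivity analyses belong in an analysis plan or on data forms, and that FMK-online access and medical records may already show tablet courses. This stands in part. The pre-test condition itself is a protocol procedure, however, and no stated rule uses those records to defer or mark a test.

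**Conclusion.** The gap is real and lies in a rule that the protocol states, not in detail left for later. The rule restricts hydrocortisone, inhaled steroid and intramuscular steroid but no other oral glucocorticoid. A patient on a tablet course can therefore be enrolled and sampled without breaching it. Current dosing is then mixed with lifelong use in both parts of the primary outcome. The proportion below 500 nmol can be raised by at most the share of patients on tablets, if a course only lowers cortisol. The correlation can move either way. It should be corrected, but no size can be put on it.

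Two stronger readings are tempting and not supported.
- A reader might infer that the correlation is inflated, since the current course adds to the lifelong total. That would require current users to be, on balance, the heavier lifelong users, and enough so to outweigh the added scatter. Nothing in the documents shows this.
- A reader might take the planning figures as a measure of the bias: 60% insufficiency in the severe-asthma study against 25% assumed here. Those figures concern adrenal insufficiency after three months of daily prednisolone. They do not concern basal cortisol during a short course, or a correlation, and they say nothing about the size of this problem.

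**What to change.** Amend the pre-test sentence in the Synacthen test section as follows.

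- **Scope.** Cover any oral glucocorticoid, consistent with the cited hospital procedure (reference 30).
- **Short course.** Defer the test until the course is finished and a stated interval has passed. The endocrinology department should set the interval, and the protocol should give it as a number.
- **Treatment that must continue.** Test the patient and flag the result. No patient stops a needed course for the test.
- **Record.** Enter the date of the last oral glucocorticoid dose with each test.
- **Analysis.** Repeat the primary analysis, both the proportion below 500 nmol and the correlation with lifelong intake, without flagged tests, and report it beside the full result.

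Merely extending the 12-hour hold to prednisolone would not be enough. It would not separate the effect of a course in progress from that of lifelong use; the deferral, the flag and the repeat analysis do that.

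The cost is one wording change, one extra data field at a procedure that already takes about 75 minutes, and one repeat analysis. The downside is a few rescheduled tests and a slightly smaller repeat analysis (80 − k patients if k of 80 are flagged).

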
Method:

Regarding 1) In the cross-sectional study, patients will receive the standard investigation and treatment at the Luftvejsklinik. This includes investigation for airway disease and possible type-2 inflammation,

treatment, etc. Measurement of their adherence and possible optimization of CRS and asthma treatment. The total amount of systemic steroids will be calculated and included in the study.

Experimental intervention (synacthen test): To investigate how prolonged use of systemic steroids and adherence affect cortisol production, all patients who agree to participate in the project will undergo a synacthen test. A synacthen test is used to assess whether the body's adrenal glands produce cortisol satisfactorily (i.e., own production). Cortisol is a hormone produced in the adrenal glands and is therefore called adrenal cortex hormone. It has a few effects, including on muscles, supportive tissues and bones, and nutrient metabolism. Therefore, the adrenal glands' ability to produce hormones is important. Reduced or absent production of adrenal cortex hormones can be seen with prolonged treatment with systemic steroids (adrenal cortex hormones). A synacthen test will be performed twice in total on all patients. The first time is at the 1st visit (preliminary examination) and the second time at the 4-month follow-up.

Ad 2) Exploratory investigation/4-month follow-up (pilot project): The experimental intervention in the follow-up involves measuring P-cortisol in patients who have now achieved high adherence (> 80%). Patients will receive standard follow-up/monitoring and treatment in the respiratory clinic.

Study population:

The study population consists of patients referred to the Luftvejsklinik, ENT, RH, for evaluation of CRS/CRSwNP/CRSnNP and with or without asthma for biological treatment. They are classified according to the type of inflammation they have (type-2 or non-type-2), whether they have CRSwNP or CRSsNP, their adherence, comorbidity with asthma, and finally the severity of the disease. All patients are given standard questionnaires to assess CRS/CRSwNP/CRSnNP and asthma (STARR-15, SNOT22, ACQ, ACT, MARS-5-L/N, Fosterscore - routine questionnaires for all patients in the Luftvejsklinik).

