In the exploratory follow-up at 4 months (pilot project), we will investigate whether good adherence (>80%) to nasal steroids versus continued poor adherence (<80%) changes in P-cortisol compared to measurement of P-cortisol from the cross-sectional study. It is not known whether good adherence (>80%) changes adrenal function. This pilot project will be used for a possible future study, where the effect of adherence will be the primary focus. Therefore, we will include all 80 patients from the cross-sectional study and divide their results into good and poor adherence.

Extraction of biological material:

A maximum of 14 ml of blood is extracted during each Synacthen test (minimum 0.5-3.5 ml maximum split tube x 2-, and 3.5-ml maximum x 2 for the first blood sample for P-cortisol baseline and for the second blood sample for P-cortisol determination). The first blood sample is collected for P-cortisol measurement before the IV injection of ACTH and a minimum of 0.5 ml and a maximum of 3.5 ml of blood is extracted. The second blood sample is collected after 30 minutes following the IV injection of ACTH, and a minimum of 0.5 ml and a maximum of 3.5 ml of blood is extracted. The material is destroyed after analysis. Therefore, no research biobank will be established.

Information from patient records:

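### The test-choice rule lets the data's distribution, not the design, decide between paired and independent tests, so it misroutes two comparisons in the 4-month follow-up

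*Protocol*

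**What the plan says.** The Statistical analysis section gives a two-branch rule: "Parametric data will be compared using paired tests, and non-parametric data using Mann-Whitney Test". It names no independent-samples test for normal data and no paired test for non-normal data. No other section limits the rule to particular comparisons.

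The follow-up is set out in three places:

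- **Method, synacthen test:** "A synacthen test will be performed twice in total on all patients". On timing: "The first time is at the 1st visit (preliminary examination) and the second time at the 4-month follow-up".
- **Secondary outcomes, item 5:** among patients whose adherence rises above 80%, the protocol looks for a "reduction in plasma cortisol of at least 8" per cent.
- **Power calculation, follow-up paragraph:** the aim is to study good adherence "versus continued poor adherence (<80%) changes in P-cortisol compared to measurement of P-cortisol from the cross-sectional study". All 80 cross-sectional patients are to be included, and the investigators will "divide their results into good and poor adherence".

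**The concern.** Pairing is fixed by the design: two values from one patient are paired, and values from different patients are not. Distribution matters only afterwards, for choosing between a t-type and a rank test. The protocol merges these two decisions into one, so two of the four possible situations get the wrong test.

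At stake is the before/after P-cortisol comparison. If P-cortisol is judged non-normal, the rule prescribes a test that ignores the link between a patient's two values and can miss a real fall without any warning. The good against poor adherence comparison has the opposite problem. If the data are judged normal, the prescribed test cannot be run on unmatched groups of unequal size, and the analyst must switch to an unplanned test. The protocol intends the pilot to inform a possible future adherence study, so a missed change could carry over into that decision.

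**Working it through.** **Step 1. Apply the rule to each planned comparison.**

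| Comparison | Design | Judged normal: rule gives | Judged non-normal: rule gives |
|---|---|---|---|
| Visit 1 vs 4 months, same patients | paired | paired test (right) | Mann-Whitney (wrong) |
| Good vs poor adherers | independent | paired test (wrong) | Mann-Whitney (right) |

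**Step 2. Mann-Whitney on paired data, no true change.** With within-patient (rank) correlation ρ, the true variance of the difference is about (1 − ρ) times what the test assumes. Nominal 5% rejection therefore becomes about 2·P(Z > 1.96/√(1 − ρ)). Simulation: 20,000 datasets per cell, lognormal P-cortisol.

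| ρ | 0.1 | 0.2 | 0.3 | 0.4 | 0.6 | 0.8 |
|---|---|---|---|---|---|---|
| Formula | 3.9% | 2.8% | 1.9% | 1.1% | 0.2% | 0.001% |
| Simulation | 3.9% | 2.9% | 2.1% | 1.3% | 0.3% | 0.0% |

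**Step 3. Power for a true 8% fall.** The 8% comes from outcome 5. The log-SD, ρ and the lognormal form are assumptions. The number of pairs is varied because the eligibility criteria restrict the follow-up to low adherers while the power section includes all 80. Each cell shows Mann-Whitney / Wilcoxon signed-rank.

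| Pairs, log-SD | ρ = 0.1 | 0.2 | 0.3 | 0.4 | 0.6 | 0.8 |
|---|---|---|---|---|---|---|
| 36, 0.35 | 15/17% | 14/19% | 12/21% | 10/23% | 7/32% | 3/56% |
| 72, 0.35 | 27/30% | 26/33% | 25/37% | 23/42% | 19/57% | 12/85% |
| 80, 0.25 | 54/57% | 54/62% | 54/68% | 54/74% | 55/89% | 58/99% |

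Hand check with normal-theory tests on the log scale, 72 pairs, log-SD 0.35, ρ = 0.8:

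- Effect: −ln(0.92) = 0.0834.
- True standard error: 0.35·√(2 × 0.2/72) = 0.0261.
- Paired power: P(Z > 1.96 − 0.0834/0.0261) ≈ 89%.
- An unpaired test takes the standard error as 0.35·√(2/72) = 0.0583, so it rejects beyond 1.96 × 0.0583 = 0.1143. Its power is P(Z > (0.1143 − 0.0834)/0.0261) ≈ 12%.

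These agree with the simulated 85% and 12%. A separate simulation with a coefficient of variation of 40% and 72 pairs gave 20% against 31% at ρ = 0.3 and 8% against 77% at ρ = 0.8.

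**Step 4. Paired test on adherence groups.** With 24 and 48 patients (assumed split) a paired t-test returns an error. With 36 and 36 in one simulated dataset, re-ordering one group's rows 5,000 times moved the paired p-value between 0.00002 and 0.012, while the independent t-test gave 0.0013. Mann-Whitney on changes, 24 vs 48, rejected 4.7% under the null, so that branch is sound.

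**Step 5. Stated figures.** The 72 rests on 25% against 8% adrenal insufficiency, and 72/0.90 = 80. Neither figure uses the test-choice sentence.

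**The case against.** The strongest reply is that the harm is narrow. It is silent only if P-cortisol is judged non-normal, analysed as a continuous measure (not as a count of patients with a fall of at least 8%), and actually put through Mann-Whitney before against after. It concerns an exploratory outcome in a pilot with no power target. The other wrong branch fails visibly. All of this stands and limits the severity.

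The sizes rest on assumed values. That also stands. The protocol fixes no clock time for sampling, and treatment may be optimised between visits, so a low correlation, and with it a small loss, cannot be excluded. In small samples both tests are weak: at 20 pairs, log-SD 0.50 and ρ = 0.4, power is about 4% against 10%.

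The follow-up sentence is awkward and might mean before/after within each adherence group. In that case paired tests would suit normal data, but the non-normal branch would still be wrong. The word versus and the division into two groups make the between-group reading the more natural one.

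Two qualifications are fair. The absence of excess false positives requires non-negative correlation; at −0.2 with 36 pairs, Mann-Whitney rejected 6.9%, though such a correlation is unlikely. Also, a direct comparison of the 0- and 30-minute cortisol values would meet the same problem, although outcome 2 as worded is an association and does not call for one.

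A final objection is that comparing change from visit 1 between groups is one legitimate analysis among several. That is true, but it matches the comparison the protocol describes.

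**Conclusion.** The concern holds: the rule is wrong as written, and the fault is minor. This is not a detail left for a later analysis plan, because the protocol states a rule and a plan that followed it would inherit the error. The consequence is confined to the exploratory 4-month follow-up. There it can hide a real within-patient change in non-normal P-cortisol, or force an unplanned change of test for normal data in adherence groups. Under the assumed lognormal model, the power loss with 72 pairs and log-SD 0.35 runs from 3 percentage points (30 − 27) at correlation 0.1 to 73 (85 − 12) at 0.8. It is small at low correlation and large only at moderate to high correlation. As worded, the primary outcome and secondary outcomes 1 to 4 do not depend on the rule, and the sample size does not change.

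**What to change.** Replace the sentence with three:

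*Within-patient comparisons use the paired t-test, or the Wilcoxon signed-rank test if the differences are non-normal. Between-patient comparisons use the independent-samples t-test, or the Mann-Whitney test if the data are non-normal. For good versus poor adherence at 4 months, the change in P-cortisol from visit 1 is compared between the groups.*

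The third sentence should also say whether change is absolute or in per cent, since outcome 5 is stated in per cent. The cost is wording only: no new data, no extra patients, no change to the 72 or 80, and all four tests are standard in the named software.
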